13. DEFINITION OF END OF TRIAL.....	69
13.1. End of Trial in the United States	69
14. SPONSOR DISCONTINUATION CRITERIA	69
15. PUBLICATION OF STUDY RESULTS	69
15.1. Communication of Results by Pfizer	69
15.2. Publications by Investigators	70
16. REFERENCES	72

LIST OF TABLES

Table 1. Overall Visit Schedule and List of Procedures.....	8
Table 2. Schedule of Activities – Study Days -1, 1, 7 & 14.....	10
Table 3. Summary of Plasma PF-06865571 PK Parameters Following Single Oral Doses in C2541001	15
Table 4. Summary of Preliminary Steady State (Day 14) Plasma PF-06865571 PK Parameters Following Multiple Oral Doses in C2541002.....	16
Table 5. Predicted Steady-State PF-06865571 Exposures with Administration of Multiple Doses of PF-06865571 Under Fed Conditions	20
Table 6. Clinical Laboratory Tests	42
Table 7. Definition of Steady State (Day 14) Plasma PK Parameters for PF-06865571.....	64

LIST OF FIGURES

Figure 1. Design of Study C2541005.....	21
---	----

APPENDICES

Appendix 1. Abbreviations	74
Appendix 2. Strong CYP3A Inhibitors and Inducers*	78

SCHEDULE OF ACTIVITIES

The schedule of activities table provides an overview of the protocol visits and procedures. Refer to [Section 6](#) and [Section 7](#) of the protocol for additional information on each procedure and assessment required for compliance with the protocol. The investigator may schedule visits (unplanned visits) in addition to those listed in the schedule of activities table, in order to conduct evaluations or assessments required to protect the well-being of the subject.

Table 1. Overall Visit Schedule and List of Procedures

Protocol Activity	Screening			Day -2	Study Day (all activities at 0H [prior to dosing] unless otherwise specified) ^a																Follow-up ^b				
	Screen 1	Screen 2	Screen 3		-1	1	2	3	4	5	6	7	8	9	10	11	12	13	14	15	16	Visit	Contact		
Visit	1	2	3		4																5	-			
Informed consent & demography	x																								
Outpatient visit (after ≥8H fast)	x																							x	
Adverse event monitoring	x			x	→	→	→	→	→	→	→	→	→	→	→	→	→	→	→	→	→	→	x	x	x
Inpatient stay at CRU				x ^c	→	→	→	→	→	→	→	→	→	→	→	→	→	→	→	→	→	→	x		
Medical & medication history	x			x																				x	x
Review drug, alcohol/tobacco use	x			x																				x	
Review prior or concomitant treatments	x			x																				x	
Review contraception use	x			x																				x	x
Physical examination (height at Screen 1 only) ^d	x			x																			x		
Body weight	x			x					x														x	x	
Triplicate, supine 12-lead ECG ^e	x								x														x	x	
Single, supine vital signs assessment ^e	x								x														x	x	
Liver fat and stiffness (via FibroScan [®]) ^f	x	x		CCI																					
Liver fat via MRI-PDFP acquisition ^g			x	x	Refer to Tabl	Refer to Tabl																	x		
Standardized meals/snacks ^h				x	Refer to Tabl	Refer to Tabl	x	x	x	x	x												x	x	
Administration of blinded IP ⁱ					Refer to Tabl	Refer to Tabl	x	x	x	x	x														
Blood sampling for:																									
- Clinical laboratory tests and serum cystatin C ^j	x				Refer to Tabl	Refer to Tabl			x															x	x
- Serum FSH (females only), HIV, HepBsAg, HepBcAb, HCVAb testing	x				Refer to Tabl	Refer to Tabl																			
- Ceruloplasmin, A1AT, HbA1c	x				Refer to Tabl	Refer to Tabl																			
- PF-06865571 PK ^k					Refer to Tabl	Refer to Tabl			x														x		
- Serum TG					Refer to Tabl	Refer to Tabl																	x		
CCI																									
- Plasma insulin ^l	x								x															x	
CCI																									

Protocol Activity	Screening			Day -2	Study Day (all activities at 0H [prior to dosing] unless otherwise specified) ^a																Follow-up ^b		
	Screen 1	Screen 2	Screen 3		-1	1	2	3	4	5	6	7	8	9	10	11	12	13	14	15	16	Visit	Contact
Days Relative to Dosing on Day 1																							
Visit	1	2	3																			5	-
Urine sampling for:																							
- Urine drug test	x																						
- Urinalysis (and microscopy, as appropriate)	x							x														x	x

- a. Day relative to start of dosing of blinded investigational product (Day 1).
- b. Follow-up visit at 7-10 days following the last dose will be an outpatient visit to the site, while follow-up contact at 28-35 days following the last dose may occur via a follow-up phone call. Phone call may be a visit if deemed necessary by the investigator.
- c. Admission to CRU should occur prior to lunch on Day -2.
- d. Full physical exam at Screen 1 and at Day 15; otherwise, limited exam if findings during previous exam or new/open AEs, if appropriate, at investigator discretion.
- e. Prior to AM dose.
- f. After ≥8H fast at outpatient visits; scans on Days -2 & 15 to occur post overnight fast of ≥8H at approximately same clock time (ie, within a practical window (±2 hours) relative to clock time of the Screening visits). **CCI**
- g. At Screen 3 visit **after** confirmation of **all** other eligibility.
- h. Meals to be provided at approximately 0H, 4H, and 10H post AM dose and snack to be provided at approximately 12H post AM dose, as specified in Section 4.4.1. Day 16 meal(s) are optional, according to clinical research unit (CRU) practice.
- i. Dosing to occur with breakfast and snack, as specified in Section 4.4.1.

CCI

- k. PK samples to be collected prior to dose.

Table 2. Schedule of Activities – Study Days -1, 1, 7 & 14

[Procedures at 0H to be completed prior to dosing or similar clock time, in the case of Day -1]

Hours Relative to Dosing at 0H ^a	0	0.5	1	2	3	4	6	8	10	12	14	16	18	24
Continued inpatient stay at CRU	→	→	→	→	→	→	→	→	→	→	→	→	→	→
Adverse event monitoring	→	→	→	→	→	→	→	→	→	→	→	→	→	→
Body weight	x													
Triplicate, supine 12-lead ECG	x													
Single, supine vital sign assessment	x													
Blinded IP administration (Days 1, 7 and 14 only)	x ^b									x ^c				
Randomization (Day 1 only)	x													
Blood sampling for:														
- Clinical laboratory tests and serum cystatin C ^d (Days 1, 7, and 14 only)	x													
CCI														
- PF-06865571 PK (Day 14 only)	x		x	x	x	x	x	x		x				
- Serum triglycerides (Days -1, 1 and 14 only) ^d	x ^f			x		x	x	x	x	x	x	x	x	
CCI														
- Plasma insulin ^{d,g}	x													
Urine sampling for:														
- Urinalysis and microscopy, as appropriate (Days 1, 7, and 14 only)	x													
Meals ^h														
- Standardized meal	x					x			x					
- Snack										x				

- a. On Day -1, nominal time to approximately match clock time of collection planned on Day 1 to permit time-matched comparison.
- b. Dosing expected to occur with breakfast.
- c. Dosing expected to occur with snack as specified in [Section 4.4.1](#).

CCI

- g. Insulin samples collected in triplicate on Day -1 and Day 14. On Day 1 and Day 7, only 1 sample will be collected.
- h. Meals/snacks to occur on all days while inpatient; identical meals/snacks on Days -2, -1, 1, 14, and 15.

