1.3.2. Dose Rationale

CCI

The dose and dosing regimen required to maximize the PD effects of PF-06865571 are not yet established. CCI

In order to fully explore the effect of DGAT2 inhibition on liver fat, PF-06865571 doses of 50 mg and 300 mg will be administered BID in this study. CCI

These total daily doses have been well tolerated with an acceptable safety profile in the ongoing multiple ascending dose study (C2541002).

Table 5. Predicted Steady-State PF-06865571 Exposures with Administration of Multiple Doses of PF-06865571 Under Fed Conditions

Total Daily Dose ^a (mg)	Regimen	Predicted C _{max} (ng/mL)	Predicted AUC ₂₄ (ng•h/mL)
100 mg	50 mg Q12H	430	2198
600 mg	300 mg Q12H	2174	13238

Abbreviations: Q12H = every 12 hours.
 a. Predicted C_{max} and AUC₂₄ were derived using a preliminary model based on available PK data from Studies C2541001 and C2541002.

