6.1. Proposed Chronology of Procedures

For the study period described below, when multiple procedures are scheduled at the same time point(s) relative to dosing, the following chronology of events should be adhered to, *where possible*.

- *12-lead ECG*: obtain prior to vital signs assessment, blood samples, and prior to dosing (refer to [Section 7.1.6](#)).
- *Vital Signs (BP and pulse rate)*: obtain after 12-lead ECG collection but prior to obtaining blood samples and prior to dosing (refer to [Section 7.1.5](#)).
- *Fasting blood samples*: after assessment of 12-lead ECG and vital signs but prior to dosing (refer to [Section 7.1.1](#)).
- *Serial blood samples for plasma PK, insulin, CCI* [REDACTED] as close as practically possible to the scheduled time (refer to [Schedule of Activities](#)).
- If the post-dose blood collection nominal time coincides with the nominal time of a meal, these blood samples should be collected just ***prior to*** meal/snack.
- *Other pre-dose procedures*: should be obtained/performed as close as possible to the scheduled time, but may be obtained before or after blood specimen collection.
- *Dosing*: must occur at the scheduled nominal time (refer to [Section 5.5](#)) and following pre-dose blood sample collection.

- ***If*** an intravenous catheter is placed for serial blood sample collections, ECGs and vital signs (pulse rate, BP) assessments should be either collected prior to the insertion of the catheter or sufficient rest period after catheter insertion introduced to minimize impact of catheter placement on these assessments.

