9.6.1. Electrocardiogram Analysis

Changes from baseline for the ECG parameters QT interval, heart rate, QTcF interval, PR interval, and QRS interval will be summarized by treatment and time.

The number (%) of subjects with maximum postdose QTcF values and maximum increases from baseline in the following categories will be tabulated by treatment:

Safety QTcF Assessment

	Borderline (msec)	Prolonged (msec)
Absolute value	≥450 - <480	≥480
Absolute change	30-<60	≥60

In addition, the number of subjects with corrected and uncorrected QT values ≥500 msec will be listed.

In addition, an attempt will be made to explore and characterize the relationship between plasma concentration and QT interval length using a PK/PD modeling approach. If a PK/PD relationship is found, the impact of subject factors (covariates) on the relationship will be examined. The analysis, if conducted, may not be reported.

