6.6.4. Electrocardiogram

Average of the triplicate measurements will be used in all analyses. Absolute values and changes from baseline in QT, heart rate, QTcF, PR, RR and QRS will be summarized by treatment and day using sponsor reporting standards. Tables will be paged by parameter. Baseline is as defined in Section 3.5.4.

Mean changes from baseline in QT, heart rate and QTcF will be plotted against study day. On each plot there will be 1 line for each treatment, all treatments on the same plot including the placebo.

In addition for baseline subtracted QT, heart rate and QTcF, the differences between each dose and placebo (dose – placebo) will be summarized (N, mean, 90% CI) and plotted (mean) for each dose and day including follow-up.

ECG endpoints and changes from baseline (QTcF, PR and QRS) will also be summarized descriptively by treatment using categories as defined in the Appendix (for QTc these correspond to ICH E14). Numbers and percentages of subjects meeting the categorical criteria will be provided. All planned and unplanned postdose timepoints will be counted in these categorical summaries. All values meeting the criteria of potential clinical concern will be listed.

Maximum absolute value (post dose) and the maximum increase from baseline for QTcF, PR and QRS will be summarized by treatment according to sponsor reporting standards.

Listings of subjects with any single post dose value > 500 msec will also be produced for QTcF.

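### Every scheduled ECG during treatment is pre-dose or follows the last dose, so the QTcF summaries and the optional concentration-QT work see at most about a quarter of the predicted peak concentration

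*Protocol*

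**What the plan says.** **Schedule.** The study-day header of protocol Table 1 reads "all activities at 0H [prior to dosing] unless otherwise specified", and the footnote on its ECG row reads "Prior to AM dose". Table 2 has a single ECG mark, at 0H, and none from 0.5H to 24H. Its title note is "Procedures at 0H to be completed prior to dosing or similar clock time, in the case of Day -1". Section 6.1 tells sites, for the 12-lead ECG, to "obtain prior to vital signs assessment, blood samples, and prior to dosing". Under Section 7.1.6 the Day 1 pre-dose triplicate is each subject's baseline.

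**Analyses.** Protocol Section 9.6.1 tabulates categories of maximum postdose QTcF and of maximum increase from baseline. It adds an attempt to "explore and characterize the relationship between plasma concentration and QT interval length using a PK/PD modeling approach" and says that this analysis, if done, may not be reported. SAP Section 3.5.4 takes the post-dose maximum by study day. SAP Section 6.6.4 states: "Maximum absolute value (post dose) and the maximum increase from baseline for QTcF, PR and QRS will be summarized by treatment". The SAP's ECG sections contain no concentration-QT model.

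**Concentrations.** Table 2 schedules PK samples on Day 14 at 0, 1, 2, 3, 4, 6, 8 and 12 h. Predicted exposures are in the Section 1.3.2 table titled "Predicted Steady-State PF-06865571 Exposures with Administration of Multiple Doses of PF-06865571 Under Fed Conditions".

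**The concern.** A maximum over post-dose ECGs is informative about a drug effect to the extent that some of those ECGs fall where concentrations are high. Here each ECG day has one scheduled time point, so the by-day maximum is simply one triplicate average, taken at the low end of the dosing interval. The Day 14 samples after 0H, which trace the rise and fall of concentration, have no scheduled ECG beside them.

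Twelve-lead ECG is part of a secondary safety endpoint. Section 1.3.1 also gives ECG safety assessment and placebo-adjusted dose-response among the reasons for a Day -1 baseline, because this is the first repeated dosing in subjects with NAFLD. What is at stake is interpretation. If an effect follows concentration, the planned summaries would show it much attenuated, and a concentration-QT slope would have to be extrapolated over most of the exposure range.

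**Working it through.** The plan gives no figure of its own on this point, so there is none to reproduce. The check has three parts.

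**1. Where the ECGs fall.**
- Day -1 and Day 1 at 0H: before any dose. Day 1 is the baseline.
- Day 7 and Day 14 at 0H: before the morning dose. Section 5.5 puts the second daily dose about 12 h after the first, so these ECGs are about 12 h after the previous evening's dose.
- Table 1 carries a further mark during the inpatient stay. Its exact day is unclear in the readable text, but footnote e makes it pre-dose on any dosing day.
- Last inpatient ECG and follow-up ECG: Table 2 shows an evening dose at 12H on Day 14, so these come about 12 h or more after the final dose.

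No scheduled ECG falls between a dose and the end of its interval.

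**2. Ceiling on the concentration at those times.** Inputs are the predicted steady-state Cmax and AUC24 in protocol Section 1.3.2. The average concentration is Cavg = AUC24/24. The minimum cannot exceed the average, so Cmin/Cmax ≤ Cavg/Cmax, whatever the shape of the curve.

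| Regimen | AUC24 (ng·h/mL) | Cavg (ng/mL) | Cmax (ng/mL) | Ceiling on Cmin/Cmax |
|---|---|---|---|---|
| 300 mg Q12H | 13238 | 13238/24 = 552 | 2174 | 552/2174 = 25% |
| 50 mg Q12H | 2198 | 2198/24 = 92 | 430 | 92/430 = 21% |

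At least three quarters of the predicted range up to Cmax therefore has no scheduled ECG. Suppose, as an assumption only, that an effect is proportional to concentration without delay. An effect of 10 msec at Cmax would then appear as at most 10 × 0.25 = 2.5 msec at 300 mg and 10 × 0.21 = 2.1 msec at 50 mg.

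**3. How far below the ceiling the trough lies.** This needs a curve shape, which the readable text does not supply. All values below are for 300 mg and match Cmax/Cavg = 2174/552 = 3.94.
- One compartment with instantaneous input: solve x/(1 − e^(−x)) = 3.94 for x = kτ. This gives x = 3.86 and Cmin/Cmax = e^(−3.86) = 2.1%.
- One compartment with first-order absorption, ka from 0.8 to 4 per h (assumed): 0.07% to 0.9%.
- Instantaneous input plus a slower second phase carrying 10% to 50% of the AUC at 0.05 to 0.1 per h (assumed): about 3% to 9%.

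These are illustrations. Only the ceilings of 25% and 21% follow from the documents.

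**The case against.** - **Postdose can mean after the first dose.** Baseline is before dosing on Day 1, so every later ECG is post-dose in that sense. This is a fair reading. A reader might infer that the tables are mislabelled, and the documents do not support that. What remains is that the label does not tell the reader that exposure was at trough.
- **The concentration-QT work is minor.** It appears only in protocol Section 9.6.1, as an attempt that may go unreported. It would be wrong to say that the SAP plans it. The post-dose maximum summaries carry no such option.
- **Unplanned ECGs count.** SAP Section 6.6.4 includes them in the categorical summaries, and some could fall near peak. They are not systematic, however, and the absolute-value trigger in Section 7.1.6 refers to scheduled ECGs, none of which is near peak.
- **Other evidence may exist.** Section 1.2.3 reports no significant cardiovascular safety pharmacology findings. Section 1.3.2 says these total daily doses were well tolerated in the multiple-dose study. The clinical background is redacted and may describe near-peak ECGs. A reader might infer that QT at peak was never examined in the programme, or that the sponsor would present a clean table as proof of no effect. The documents show neither. This lowers the urgency but does not change what this trial's own ECGs can show.
- **Re-timing is more than a change of two cells.** This stands. With the Day 1 pre-dose baseline kept for all ECGs, a post-breakfast Day 14 ECG would be compared with a fasting value.

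**Conclusion.** The point holds as a mismatch between the ECG schedule and the ECG analyses. The QTcF summaries and the optional concentration-QT exploration rest on scheduled ECGs at no more than about 25% (300 mg Q12H) and 21% (50 mg Q12H) of predicted Cmax. Those ceilings assume that the model-predicted exposures are right and that the pre-dose level is the trough. They need no assumption about curve shape.

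A reader might go further and infer that the ECGs see practically no drug, with trough below 1% of peak. The documents do not support that. The figure depends on an assumed absorption rate and a one-compartment curve, and other plausible shapes give 2% to 9%.

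This does not affect the primary endpoint and does not invalidate the safety data. It is an inexpensive improvement that would let the planned ECG analyses see near-peak exposure, or at least be described for what they are.

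**What to change.** Reconcile the ECG schedule with the planned ECG analyses.

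**Preferred.**
- Move the planned Day 14 triplicate from 0H to an existing Day 14 post-dose PK sample time near the Tmax known to the sponsor, keeping the ECG ahead of the blood draw. The readable text gives no Tmax, so the sponsor must choose the time.
- Move the Day -1 triplicate to the same clock time. Table 2 already aligns Day -1 clock times with Day 1 and requires identical meals on Days -1 and 14, so the comparison is controlled for food and time of day.
- Amend Table 1 footnote e, the Table 2 ECG row and Section 6.1 to match.
- In protocol Section 7.1.6 and SAP Section 3.5.4, define the time-matched Day -1 value as baseline for that Day 14 ECG. Keep the Day 1 pre-dose baseline for the others. Report the placebo-adjusted difference, which SAP Section 6.6.4 already provides for by dose and day.
- The QTcF monitoring thresholds in Section 7.1.6 also refer to baseline. How they apply to the re-timed ECG must be stated; that is for the sponsor's medical staff, and no rule is proposed here.

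**Cost.** No added ECG or blood draw, and the subjects are already confined. The Day 14 pre-dose ECG is lost, although Day 7 keeps one, and several sections in both documents need amending.

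**If the schedule is kept.** Label the SAP Section 6.6.4 summaries as trough ECGs, state that they do not address peak exposure, and remove the concentration-QT analysis from protocol Section 9.6.1. This changes text only.

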1. INTRODUCTION

Diacylglycerol acyltransferases (DGATs) catalyze the terminal step in triglyceride (TG) synthesis; specifically, the esterification of a fatty acid (FA) with diacylglycerol (DAG) resulting in the formation of TG.¹ In mammals, 2 structurally unrelated DGAT enzymes (DGAT1 and DGAT2) have been characterized. DGAT1 is highly expressed in the intestine and plays a central role in fat absorption.² DGAT2 is highly expressed in liver and adipose.³ In preclinical models, blockade of hepatic DGAT2 using antisense oligonucleotides results in both down-regulation of the expression of multiple genes encoding proteins involved in lipogenesis and parallel induction in oxidative pathways.^{4,5} The net result of these changes is a decrease in the levels of hepatic DAG and TG lipid which, in turn, reduces hepatocyte lipid burden and decreases hepatic very low density lipoprotein (VLDL) TG secretion.^{5,6} PF-06865571 is an oral, small molecule DGAT2 inhibitor that is postulated to decrease hepatic TG synthesis and hepatic lipid burden in non-alcoholic fatty liver disease (NAFLD) and non-alcoholic steatohepatitis (NASH).

The current study is the first designed to evaluate the safety, tolerability, pharmacokinetics (PK), and pharmacodynamics (PD) following administration of repeated (up to 14 days) oral doses of PF-06865571 in the fed state to adult subjects with NAFLD.

1.1. Mechanism of Action/Indication

PF-06865571 is an oral, small molecule DGAT2 inhibitor that is currently being developed for the treatment of NASH.

1.2. Background

NAFLD is estimated to affect at least 25% of the general population in Western countries, while the prevalence of NASH is estimated at 3 to 5%.⁷ NAFLD is strongly associated with obesity, insulin resistance, hypertension, and dyslipidemia and is now regarded as the hepatic manifestation of metabolic syndrome.⁸ NAFLD describes a spectrum of liver conditions whose dominant feature is hepatic TG accumulation.⁹ NASH is diagnosed clinically by liver biopsy demonstrating steatosis, inflammation, and ballooning of liver hepatocytes, often with varying degrees of fibrosis. NASH progresses with increasing degrees of fibrosis, with cirrhosis and/or hepatocellular carcinoma developing in a subset of patients.¹⁰ Although the factors that promote TG deposition in the liver and transition from steatosis to NASH and cirrhosis in humans have not been clearly defined, hepatic steatosis arises from an imbalance between TG acquisition and removal.¹¹ Although there is a growing body of evidence that demonstrates the urgent need for therapies for NASH, there are no currently approved therapies for the treatment of NASH.¹⁰

Hepatic TGs are derived from 3 principal sources: de-novo lipogenesis (DNL), re-esterification from FA supplied by the adipose, and dietary intake.¹¹ While the largest contribution to the hepatic TG pool appears to be derived from lipolytic products originating in adipocytes, the lipogenic pathway plays an important role in the development of NAFLD and progression to NASH.¹² The contribution of DNL to disease progression in NAFLD is supported by analyzing the FA composition of TGs in subjects with and without NAFLD. Data demonstrate an increased level of saturated FAs in those with NAFLD, implicating the

DNL pathway as an important contributor to hepatic steatosis as saturated FAs represent the primary product of DNL.¹² These findings are consistent with the increased inclusion of DNL-derived TGs in VLDL particles in NAFLD where 15% of TG produced originated from DNL compared to only 2 to 5% in normal subjects consuming a typical Western diet.¹² Additionally, elevated rates of hepatic DNL have been reported to be a distinctive characteristic of NAFLD.¹³ Human subjects with elevated liver fat showed a more than 3-fold increase in the rate of hepatic DNL relative to subjects with normal liver fat, but no differences between the groups were detected in adipose free fatty acid (FFA) flux or in production of VLDL from FFAs. Consequently, when comparing the absolute sources of FAs incorporated into VLDL-TG, elevated hepatic DNL was the only source significantly elevated in subjects with high liver fat.¹³

Based on observations in nonclinical studies conducted with PF-06865571, it is hypothesized that DGAT2 inhibition will impact both physiological drivers contributing to NASH via direct inhibition of liver TG synthesis, as well as adaptive responses leading to reduction in hepatic DNL.

